6.13.2.1. Common Adverse Events

The percentages of participants with TEAEs will be summarized by treatment using the MedDRA PT for the common TEAEs (occurred in $\geq 1\%$ before rounding in any column in the table).

6.13.2.2. Deaths, Other Serious Adverse Events, and Other Notable Adverse Events

The number and percentage of participants reported with an SAE during the treatment period will be summarized by treatment using the MedDRA PT. A listing of SAEs will be provided.

The number and percentage of participants who permanently discontinued from study treatment due to an AE (including AEs that led to death) during the treatment period will be summarized by treatment using MedDRA PT. Events will be ordered by decreasing frequency in all treatment groups for both AE and SAE.

6.13.3. Clinical Laboratory Evaluation

As described more fully in compound level safety standards and in the laboratory-related PhUSE white papers (PhUSE 2013, 2015), the clinical laboratory evaluations will be summarized as described in [Table KGAK.6.9](#).

Table KGAK.6.9. Analysis for Clinical Laboratory Evaluations

Analysis	Population
Box plots of observed values by visit	mS
Box plots for change values by visit	
Change from baseline to last observations. ANCOVA model with treatment and baseline value in the model	mS
Scatter plots of baseline-by-maximum values and baseline-by-minimum values	mS
Treatment-emergent abnormal high lab values (i.e., participants shifting from a normal/low maximum baseline value to a high maximum postbaseline value) or abnormal low lab values (i.e., participants shifting from normal/high minimum baseline value to a low minimum postbaseline value)	mS

Analysis	Population
Shift tables showing the number of participants who shift from each category of maximum (minimum) baseline observation to each category of maximum (minimum) postbaseline observation. Here categories may be low, normal, or high with cut-offs defined in the compound level safety standards.	mS
Listing of abnormal findings for laboratory analyte measurements, including qualitative measures	All Enrolled

Abbreviations: ANCOVA = analysis of covariance; mS = Modified Safety Population.

6.13.4. Vital Signs and Other Physical Findings

As described more fully in compound level safety standards and in the laboratory-related PhUSE white papers (PhUSE 2013, 2015), vital signs will be summarized similarly to the clinical laboratory evaluation ([Table KGAK.6.10](#)). For vital signs, treatment-emergent low and high are based on a combination of a specified value and a change or percentage change as defined in the compound level safety standards.

Table KGAK.6.10. Analysis Related to Vital Signs

Analysis	Population
Box plots for observed values by visit	mS
Box plots for change from baseline values by visit	mS
Scatterplots of baseline-by-maximum values and baseline-by-minimum values	mS
Tables with the number and percentage of subjects who shift from normal/high to low (i.e., treatment-emergent low) and the number and percentage of subjects who shift from normal/low to high (i.e., treatment-emergent high); the limits are defined in the compound level safety standards	mS

Abbreviation: mS = Modified Safety Population.

6.13.5. Immunogenicity

An individual sample is potentially examined multiple times in a hierarchical procedure to produce a sample antidrug antibody (ADA) assay result and may yield a sample neutralizing ADA (NAb) assay result. Treatment-emergent ADAs (TE-ADAs) are defined as those with a titer 2-fold (1 dilution) greater than the minimum required dilution if no ADAs were detected at baseline (treatment-induced ADA) or those with a 4-fold (2 dilutions) increase in titer compared to baseline if ADAs were detected at baseline (treatment-boosted ADA). A participant is considered TE-ADA positive when at least 1 postbaseline ADA sample meets the definition of TE-ADA. A participant is evaluable for TE-ADA if there is at least 1 nonmissing test result for ADA for both the baseline and the postbaseline visits.

Compound level safety standards will be followed in the analyses of immunogenicity. Listings of immunogenicity assessments will be provided for the Safety Population. The summary of TE-ADA and NAb status will be produced for the Modified Safety Population, where the postbaseline period for reporting is the same as described for AEs in Section [6.13.2](#). Additional assessments of the relationship between immunogenicity and efficacy will be performed as part of the integrated analysis including other Phase 3 lebrikizumab AD trials.

6.13.6. Special Safety Topics including Adverse Events of Special Interest

This section includes areas of interest whether due to observed safety findings, potential findings based on drug class, or safety topics anticipated to be requested by a regulatory agency for any reason. In general, potential adverse events of special interest (AESIs) relevant to these special safety topics will be identified by 1 or more Standardized MedDRA Query(ies) (SMQ[s]), by a Lilly-defined MedDRA PT listing based upon the review of the most current version of MedDRA, or by treatment-emergent relevant laboratory changes, as described below. Additional special safety topics may be added as warranted.

Unless otherwise specified, the special safety topic will be summarized for the Modified Safety Population during the Treatment Period as described in Section 6.13.

Full details of the search terms and rules for deriving special safety topic in each of the sections below are described in the compound level safety standards along with information about the types of summaries and listings to be provided. In the event that the listing of terms or analysis changes for a special safety topic, it will be documented in the compound level safety standards that will supersede this document; it will not warrant an amendment to the individual study SAP.

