9.3. Populations for Analyses

The following participant populations are defined:

Population	Description
Intent-to-Treat (ITT)	All participants assigned to study drug, regardless of whether they take any doses of study drug, or if they took the correct study drug. Participants will be analyzed according to the treatment group to which they were randomly assigned.
Per Protocol (PP)	All participants in the safety population who complete the Week 16 (Visit 10) evaluation without any significant protocol violations.
Safety	All participants randomly assigned to study drug and who take at least 1 dose of study drug. Participants will be analyzed according to the study drug they actually received.
Pharmacokinetic Analysis	All randomized participants who received at least 1 full dose of

	study drug and at least 1 postbaseline evaluable PK sample.
Immunogenicity Analysis	A participant is evaluable for treatment-emergent ADA if there is at least 1 non-missing test result for ADA for both the baseline and the postbaseline visits.

Abbreviations: ADA = anti-drug antibody; PK = pharmacokinetic.

The PP population will include participants in the safety population without significant protocol deviations (i.e., any participant or investigator activity that could have possibly interfered with the therapeutic administration of the study drug or the precise evaluation of the study drug efficacy). Significant protocol deviations include the following:

- Used prohibited treatment that required permanent discontinuation of the study drug (see Section 7.1.2)
- Missed either one or both Week 12 or Week 16 study visits (Visits 8 and 10)
- Have not been compliant with the dosing regimen (i.e., participants must receive 80% of the expected injections of study drug and both of the vaccines during participation in the study)
- Exceeded the out-of-the-visit window at the Week 16 visit (Visit 10) by more than ± 7 days

Additional significant protocol deviations may be specified in the Statistical Analysis Plan (SAP) prior to unblinding.

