9.4.5. Safety Analyses

All AEs occurring during the study will be recorded and coded using the MedDRA dictionary. Treatment-emergent AEs (TEAEs) are defined as AEs with an onset date on or after the date of the first injection of study drug. TEAEs will be summarized by treatment group, including the number of participants reporting an event, system organ class, preferred term, severity, relationship to study drug, and seriousness for the safety population. All SAEs as well as AEs that led to study discontinuation will be listed by participant.

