6.1.1. Analysis Populations

Analysis populations are defined in [Table KGAK.6.1](#) along with the analysis they will be used to conduct. [Table KGAK.6.2](#) describes the treatment groups and the comparisons for each study period and the analysis population.

Table KGAK.6.1. Analysis Populations

Population	Description
All Entered Patients	All participants who signed informed consent. Participant flow will be summarized.
Intent-to-Treat (ITT) Population	All randomized participants, even if the participant does not take the assigned treatment, does not receive the correct treatment, or otherwise does not follow the protocol. Participants will be analyzed according to the treatment to which they were assigned.
Modified Intent-to-Treat (mITT) Population	ITT population excluding all participants from Site 1883 ^a and Site 1827 ^b . Unless otherwise specified, efficacy and health outcomes analyses will be conducted on this population.
Safety Population	All randomized participants who received at least 1 dose of study treatment.
Modified Safety Population	Safety population excluding all participants from Site 1883 and Site 1827. Safety analyses will be conducted on this population.
Per-Protocol Set (PPS)	All Safety Population participants without any significant protocol deviations. Significant protocol deviations include (but not limited to) the following:

Population	Description
	
 Used prohibited treatment that required permanent discontinuation of the study drug (see Protocol Section 7.1.2) that is systemic rescue medication Missed either 1 or both Week 12 or Week 16 study visits (Visits 8 and 10) Had not been compliant with the dosing regimen (i.e., participants must receive 80% of the expected injections of study drug and both of the vaccines during participation in the study) Exceeded the out-of-the-visit window at the Week 16 visit (Visit 10) by more than 7 days 
Additional significant protocol deviations that could possibly have impact on precise evaluation of the primary objective will be recorded in a separate tracker and participants with these significant protocol deviations will also be excluded from the PPS.
 
Primary analyses for vaccine response primary endpoints will use the PPS. Analyses for IGA0/1 and EASI 75 will be repeated using the PPS.

Abbreviations: EASI = Eczema Area and Severity Index; EASI 75 = $\geq 75\%$ reduction from baseline in EASI score; IGA = Investigator's Global Assessment.

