- a The rationale for excluding participants from Site 1883 is in a directed site audit triggered by statistically implausible data in Study KGAD/AD06 at this study site, and the same site was also included in this study, KGAK/AD18. It was determined that some or all of the study participants at this site did not meet the eligibility criterion of having moderate-to-severe atopic dermatitis, and associated data was unreliable.
- b The rationale for excluding participants from Site 1827 is a clinical site audit of lebrikizumab atopic dermatitis studies KGAK/AD18 and KGAA/AD07 at this site resulted in critical findings. It was determined by the audit that there was a lack of source documentation needed to substantiate eligibility for all participants enrolled at this site. Additionally, a quality issue was opened that participant data regarding their moderate-to-severe atopic dermatitis is either unreliable, inconsistent, and/or missing source documentation.

Table KGAK.6.2. Treatment Groups and Comparisons and Analysis Population

Study Period	Analysis Population	Treatment Groups	Abbreviation	Inferential Comparisons When Applicable
Treatment Period	mITT; Safety; Modified Safety; PPS	Placebo; Lebrikizumab 250 mg Q2W	PBO; LEB250Q2W	LEB250Q2W vs PBO

Abbreviations: LEB = lebrikizumab; mITT = modified intent-to-treat; PBO = placebo; PPS = per protocol set; Q2W = every 2 weeks; vs = versus.

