6.13.2. Adverse Events

A TEAE is defined as an event that first occurred or worsened in severity after baseline (date of first injection). The MedDRA Lowest Level Term (LLT) will be used in the treatment-emergent computation. The maximum severity for each LLT during the baseline period will be used as baseline. The treatment period will be included as postbaseline for the analysis. For events with a missing severity during the baseline period, it will be treated as “mild” in severity for determining treatment-emergence. Events with a missing severity during the postbaseline period will be treated as “severe” and treatment-emergence will be determined by comparing to baseline severity. For events occurring on the day of first taking study medication, it will be assumed to be posttreatment.

The planned summaries for AEs are provided in [Table KGAK.6.8](#) and are described more fully in compound level safety standards and in the AE-related PhUSE white paper (Analysis and Displays Associated with Adverse Events: Focus on Adverse Events in Phase 2-4 Clinical Trials and Integrated Summary Document [PhUSE 2017]).

Summary tables as described in [Table KGAK.6.8](#) will be presented for the following periods/analysis populations as indicated. Summary tables will include the number and percentage of participants reporting an event. For events that are gender-specific (as defined by MedDRA), the number of participants at risk will include only participants from the given gender.

Table KGAK.6.8. Summary Tables/Listing Related to Adverse Events

Analysis	Population (Section 6.1.1)
Overview of AEs	mS, S
Summary of TEAE by PTs	mS
Summary of TEAE by PTs occurring in $\geq 1\%$ of participants	mS
Summary of TEAE by PTs within SOC	mS
Summary of TEAE PTs by maximum severity	mS, S
Summary of SAE by PT within SOC	mS, S
Summary of AEs leading to treatment discontinuation by PT with SOC	mS
Summary of TEAE possibly related to study drug by PTs within SOC	mS

Analysis	Population (Section 6.1.1)
Listing of SAEs (including Death)	ITT
Listing of primary AEs leading to study treatment discontinuation	ITT
Listing of TEAE (for Japan submission only)	S
Listing of AE for Participants from Site 1883 and Site 1827	-

Abbreviations: AE = adverse event; ITT = Intent-to-Treat; mS = Modified Safety Population; PT = preferred term; SAE = serious adverse event; S = Safety Population; SOC = System Organ Class; TEAE = treatment-emergent adverse event.

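### The SAP summarizes TEAEs by system organ class and drug-related TEAEs only without Sites 1883 and 1827, although Protocol 9.4.5 places both summaries in the full safety population

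*SAP*

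**What the plan says.** Protocol 9.4.5 plans TEAE summaries by treatment group covering "system organ class, preferred term, severity, relationship to study drug, and seriousness for the safety population". Protocol 9.3 defines that population as "All participants randomly assigned to study drug and who take at least 1 dose of study drug", with no exclusion by site. For events behind early stopping, 9.4.5 asks for a listing: "All SAEs as well as AEs that led to study discontinuation will be listed by participant".

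SAP 6.1.1, Table KGAK.6.1, adds mS: "Safety population excluding all participants from Site 1883 and Site 1827. Safety analyses will be conducted on this population". SAP 6.13 instead bases safety evaluations on mS and S together.

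Table KGAK.6.8 in SAP 6.13.2 then assigns populations row by row. The AE overview, TEAE preferred terms by maximum severity, and SAEs by preferred term within SOC are on mS and S. TEAEs by preferred term within SOC and TEAEs possibly related to study drug are on mS only. So is the row "Summary of AEs leading to treatment discontinuation by PT with SOC". For special topics, SAP 6.13.6 says that, unless otherwise specified, "the special safety topic will be summarized for the Modified Safety Population during the Treatment Period", and the by-arm summaries in Tables KGAK.6.11 to KGAK.6.19 follow that default.

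**The concern.** Participants at the two sites received study drug or placebo. Doubt about whether they had moderate-to-severe disease does not undo that exposure, and a safety population normally keeps everyone exposed. The protocol promised by-arm counts by SOC and by relationship to study drug for all of them. Under Table KGAK.6.8 those counts exist only with the two sites removed, and the Fisher's exact tests and odds ratios that SAP 6.13.2 plans for these summaries carry the same restriction.

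The SAP also gives no rule for the split. It runs three AE summaries on S as well as mS, so it treats these sites' AE data as fit to show there, but it does not say why SOC and relatedness differ. At stake is whether a reader can see, by arm and for all dosed participants, how events distribute over organ systems and how many were judged drug-related.

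**Working it through.** The point rests on no figure stated in the plan, so there is none to reproduce. The check sets the protocol commitment against the SAP rows.

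| Item named in Protocol 9.4.5 | By-arm summary on S in SAP Table KGAK.6.8? |
|---|---|
| Preferred term | Yes, preferred terms by maximum severity |
| Severity | Yes, same row |
| Seriousness | Yes, SAEs by preferred term within SOC |
| SOC, all TEAEs | No, mS only |
| Relationship to study drug | No named summary, mS only |

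The S table of SAEs by SOC does not fill the SOC gap, because it covers serious events only. The severity table on S does not fill it either. A participant with two terms in one organ class counts once in the class total, so that total cannot be obtained by adding preferred-term rows. The AE overview on S might show a drug-related total, but the SAP does not state its rows. Even if it does, it would not be by term within SOC.

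**Possible size.** The documents do not give the number at the two sites. As an illustration, assume all 240 planned participants (SAP 5.2) were dosed, that k of them were at the two sites, and that m participants report a given term, spread without regard to site. The chance that the mS table loses at least one of them is

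1 − C(240 − k, m) / C(240, m).

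For k = 10 and m = 3: 1 − (230 × 229 × 228)/(240 × 239 × 238) = 1 − 12,008,760/13,651,680 = 0.120.

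| k (assumed) | Share of 240 | m = 3 | m = 5 |
|---|---|---|---|
| 5 | 2.1% | 6% | 10% |
| 10 | 4.2% | 12% | 19% |
| 20 | 8.3% | 23% | 36% |
| 40 | 16.7% | 42% | 60% |

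These are chances that a count changes. They do not show bias, and they do not show that any conclusion would change.

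**The case against.** The case for the plan is substantial. The audit footnotes to Table KGAK.6.1 give real reasons for mS. At Site 1883 some or all participants "did not meet the eligibility criterion of having moderate-to-severe atopic dermatitis, and associated data was unreliable", and at Site 1827 the source needed to support eligibility was missing. The mS population entered in SAP Version 2, approved before Week 16 unblinding, and the revision history logs the change section by section. Protocol 9.4.1 allows analysis changes that do not alter a principal feature to be made without an amendment if they are described and justified. Events at the two sites also stay visible. There is an AE listing for those sites, ITT listings of SAEs and of AEs leading to stopping study treatment, and S listings for conjunctivitis and for opportunistic, serious, herpes and parasitic infections.

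Most of this stands. It supports mS as the main safety population, and the timing gives no ground to infer a data-driven exclusion. It does not explain why SOC and relatedness lack an S version when three neighbouring rows have one. Nor does it remove the disagreement between SAP 6.1.1 and 6.13. Listings show events but give no comparison of proportions by arm.

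A reader might infer three stronger things, and the documents support none of them:

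- That all by-term TEAE summaries lose these participants. Preferred terms by maximum severity are on S.
- That the mS-only summaries of discontinuation events and special topics breach the protocol. Section 9.4.5 asks only for a listing of events leading to study discontinuation and names no special-topic summary.
- That the audits questioned efficacy data alone, so the safety data are sound. The Site 1883 footnote carries no such limit.

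**Conclusion.** The point holds for two rows of Table KGAK.6.8. TEAEs by preferred term within SOC and possibly drug-related TEAEs have no Safety Population version, contrary to Protocol 9.4.5 and out of line with SAP 6.13. The other items named in 9.4.5 are met on S.

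For discontinuation events and special topics, the restriction is a gap in completeness. It also fits poorly with the two-population statement in SAP 6.13, to which 6.13.6 refers back. It is not a departure from 9.4.5. The gap matters most for the events of special interest in Protocol 8.3.6 that Tables KGAK.6.13 and KGAK.6.14 summarize: conjunctivitis, and herpes and parasitic infections. Their grouped totals cannot be rebuilt from preferred-term rows, for the same reason as SOC totals.

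The size is unknown. Any figure rests on an assumed number at the two sites, and the effect could be negligible if few were dosed there. The change is worth making because the commitment is explicit and the remedy is cheap.

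**What to change.** 1. In Table KGAK.6.8, add S beside mS for TEAEs by preferred term within SOC and for TEAEs possibly related to study drug.
2. Reconcile the statement in Table KGAK.6.1 that safety analyses use mS with the statement in SAP 6.13 that they use mS and S. Say which tables use which population and why.
3. Report the number of dosed participants excluded per arm.
4. As a sensitivity analysis, add S to the summary of AEs leading to treatment discontinuation and to the by-arm conjunctivitis, herpes and parasitic infection summaries in Tables KGAK.6.13 and KGAK.6.14.

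The cost is a few extra tables from programs that already exist. The drawback is that the S tables include data the audits questioned, so the mS tables should stay next to them and readers can compare results with and without the two sites.

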6.13.6.1. Hepatic Safety

Hepatic labs include alanine aminotransferase (ALT), aspartate transaminase (AST), total bilirubin (TBL), and serum alkaline phosphatase (ALP).

Table KGAK.6.11. Summary Tables Related to Hepatic Safety

Analysis	Population
ALT and AST: The number and percentage of subjects with a measurement greater than or equal to 3 times (3 \times), 5 times (5 \times), and 10 times (10 \times) the performing lab upper limit of normal (ULN) during the treatment period for all subjects with a postbaseline value and for subsets based on various levels of baseline value TBL and ALP: The number and percentage of subjects with a measurement greater than or equal to 2 times (2 \times) the performing lab ULN during the treatment period will be summarized for all subjects with a postbaseline value and for subsets based on various levels of baseline value	mS
Plot of maximum post-baseline ALT vs maximum postbaseline total bilirubin	Modified Safety Population for All Periods: ever on lebri and never on lebri

Abbreviations: ALP = serum alkaline phosphatase; ALT = alanine aminotransferase; AST = aspartate transaminase; lebri = lebrikizumab; mS = Modified Safety Population; TBL = total bilirubin.

